## 7.3. Mucositis or “hand-foot” syndrome

In case of grade 3-4 toxicity, a reduction in dosage of 25% of continuous 5FU will be carried out for the subsequent cycles.

## 7.4. Cardiac toxicity

In case of unstable angina or myocardial infarction, the protocol will be discontinued.

## 7.5. Increase of bilirubin

In case of elevation of bilirubin, it is suggested to exclude an obstruction of the biliary tract or stent or progressive disease and postpone chemotherapy. If bilirubin is >1.5xULN, irinotecan is not recommended. If chemotherapy is medically indicated, it is necessary to provide a dose adjustment of irinotecan at investigator's discretion.

## 7.6. Other toxicities

Any other toxicity grade 2 or greater, except anemia and alopecia, can justify a reduction of dose if medically indicated, for example reduction of irinotecan to 150 mg/m^2 and/or oxaliplatin to 60mg/m^2 and/or 5FU of 25% depending of the type of adverse event.

# 8. ADVERSE EVENTS: LIST AND REPORTING REQUIREMENTS

Adverse event (AE) monitoring and reporting is a routine part of every clinical trial. The following list of AEs (Section 8.1) and the characteristics of an observed AE (Section 8.2) will be collected. The principal investigator will review all serious adverse events. Additionally, serious adverse effects will be reported to our IRB.

Safety and tolerability will be assessed according to the NIH/NCI CTC version 4.0. Please refer to: [http://ctep.cancer.gov/protocolDevelopment/electronic\\_applications/ctc.htm](http://ctep.cancer.gov/protocolDevelopment/electronic_applications/ctc.htm)

## 8.1 Comprehensive Adverse Events and Potential Risks List (CAEPR)

This list corresponds to the list of grade 3 and 4 adverse events that occurred in more than 5% of the patients with adenocarcinoma of the pancreas that received FOLFIRINOX in the metastatic locally advanced setting.

Hematological adverse effects:

Neutropenia - 45%  
Thrombocytopenia – 9%  
Anemia – 8%  
Febrile neutropenia – 5%

Non-hematological side effects:

Fatigue - 24%  
Vomiting -15%  
Diarrhea - 13%  
Peripheral neuropathy - 9%  
Elevated alanine aminotransferase - 7.3%  
Thromboembolism - 6.6%  
Alopecia - 11.4% (grade 2)

## 8.2 Adverse Event Characteristics

- **CTCAE term (AE description) and grade:** The descriptions and grading scales found in the revised NCI Common Terminology Criteria for Adverse Events (CTCAE) version 4.0 will be utilized for AE reporting. All appropriate treatment areas should have access to a copy of the CTCAE version 4.0. A copy of the CTCAE version 4.0 can be downloaded from the CTEP web site ([http://ctep.cancer.gov/protocolDevelopment/electronic\\_applications/ctc.htm](http://ctep.cancer.gov/protocolDevelopment/electronic_applications/ctc.htm))
- **“Expectedness”:** AEs can be ‘Unexpected’ or ‘Expected’ (see Section 7.1 above) for expedited reporting purposes only. ‘Expected’ AEs (the ASAEL) are listed under section 8.1 (CAEPR).
- **Attribution of the AE:**
  - Definite – The AE is *clearly related* to the study treatment.
  - Probable – The AE is *likely related* to the study treatment.
  - Possible – The AE *may be related* to the study treatment.
  - Unlikely – The AE is *doubtfully related* to the study treatment.
  - Unrelated – The AE is *clearly NOT related* to the study treatment.

## 8.3 Laboratory Test Abnormalities

Abnormal laboratory values or test results constitute adverse events only if they induce clinical signs or symptoms, are considered clinically significant, or require therapy. Clinically significant laboratory results are those requiring a change in the patient’s treatment, further diagnostic testing or specific clinical intervention (i.e., treatment delays or dose modifications, etc). Therefore, the following laboratory abnormalities should be captured on the nonserious AE CRF page or SAE Report Form (paper or electronic) as appropriate:

- Any laboratory test result that is clinically significant or meets the definition of an SAE
- Any laboratory abnormality that required the subject to have study drug discontinued or interrupted
- Any laboratory abnormality that required the subject to receive specific corrective therapy

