### **12.4 Analysis of Endpoints**

- a) Response rates defined by RECIST criteria, version 1.1. Best response rates to treatment will be summarized in 4 ordinal categories: complete response, partial response, stable disease or progression of disease.
- b) Data on progression-free survival (initiation date of therapy to disease progression or death) and overall survival (initiation date of therapy to death) will be collected. Patients alive and free of progression by the time of analysis will be censored and patients who progress or died will be classified as “failures” for statistical analysis purpose. Kaplan-Meier methodology will be used to summarize time-to-event variables.
- c) Safety analysis will be analyzed by collecting date on treatment-related morbidity and mortality. We will collect data on frequency, type and severity of all adverse events that occur on or after Cycle 1, Day 1 according to National Cancer Institute Common Toxicity Criteria for Adverse Events (NCI CTCAE; Version 4.0). Results will be presented as a table.

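### Section 8.3 admits laboratory adverse events by symptoms, action or therapy and not by CTCAE grade, so the 12.4(c) safety table can under-report laboratory toxicity, chiefly grade 1–2 values and ALT/AST rises

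*Combined protocol and SAP*

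**What the plan says.** Section 8.3 sets the entry rule for laboratory findings: "Abnormal laboratory values or test results constitute adverse events only if they induce clinical signs or symptoms, are considered clinically significant, or require therapy". Clinical significance is itself defined by response. A result qualifies if it calls for a change in treatment, "further diagnostic testing or specific clinical intervention". CTCAE grade is not among the criteria.

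Section 12.4(c) collects the "frequency, type and severity of all adverse events that occur on or after Cycle 1, Day 1", graded by CTCAE v4.0, and presents the results as a table. Section 12 plans no tabulation of laboratory values by grade, so the table inherits the 8.3 rule.

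Section 8.1 gives outside rates from FOLFIRINOX in pancreatic adenocarcinoma: "This list corresponds to the list of grade 3 and 4 adverse events that occurred in more than 5% of the patients". Anemia is listed at 8% and raised ALT at 7.3%. Section 8.2 uses this list to sort events into expected and unexpected, "for expedited reporting purposes only".

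The Section 10 calendar schedules a blood count and a chemistry panel that includes AST and ALT, before the study and at each of cycles 1 to 12.

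**The concern.** Safety is the secondary objective in the synopsis, and adverse effects are a secondary endpoint in Section 2.2. A reader of a CTCAE table takes its laboratory rows to show how many patients reached each grade. Under 8.3 they show something else. Of two patients with the same ALT, one whose investigator ordered further tests is counted. The other, with no symptoms and no response to the result, is not.

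The rows therefore mix toxicity with local management. Relative to a count by grade, the rule can remove patients but cannot add any, so the error runs one way, toward fewer events. The trial has one arm, so there is no concurrent group subject to the same filter.

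**Working it through.** **1. The denominator.** Section 12.2 gives 28 evaluable patients: stop if 3 or fewer of 12 respond, failure if 11 or fewer of 28 respond. With b(x; 12, p) the binomial probability of x responses among 12, the chance of passing both stages is

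Σ (x = 4 to 12) b(x; 12, p) × P(Bin(16, p) ≥ 12 − x).

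This is 0.0954 at p = 0.30 and 0.8020 at p = 0.50. The design meets its stated alpha of 0.10 and power of 0.80. The figure of 28 is not in dispute and serves here only as a denominator.

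**2. Which values 8.3 lets through.** A value enters the table if the protocol attaches an action to it.

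| Analyte | Text that attaches an action | Result under 8.3 |
|---|---|---|
| Neutrophils | 7.1: hold and dose rules below the day-1 threshold. 7.1b: febrile, prolonged grade 4, or with infection; growth factor if grade 3/4 recurs after a first reduction. 9.1.4: interruption below 1000/mm³ | Largely captured. A first uncomplicated nadir that recovers by day 1 is not in 7.1b and is reached only by 9.1.4 |
| Platelets | 7.1: day-1 threshold. 7.1b: grade 3–4 | Captured when severe |
| Bilirubin | 7.5: work-up and postponement | Captured |
| Hemoglobin | None in 7.1; excepted in 7.6; 9.1.4 lists a value below 8 g/dL among reasons to reduce irinotecan | Largely captured when severe, but the sections conflict |
| ALT/AST | No specific rule in Section 7; 7.6 only | Captured only if the investigator acts, tests or treats |

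The 7.6 text is "Any other toxicity grade 2 or greater, except anemia and alopecia, can justify a reduction of dose if medically indicated". That is permissive for ALT/AST and excepts anemia. Most grade 1–2 values of any analyte have no action attached. The exception is a day-1 count below the 7.1 thresholds, which triggers a hold whatever its grade.

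**3. How much could be lost at grade 3–4.** Let f be the share of grade 3–4 cases that pass 8.3. The documents do not give f, so it is an assumption shown over its full range. At a listed rate r:

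- expected cases in the table = 28 × r × f
- probability that the table shows none = (1 − r × f)^28

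| f | Anemia (r = 0.08): expected | P(none) | ALT (r = 0.073): expected | P(none) |
|---|---|---|---|---|
| 1 | 2.24 | 0.097 | 2.04 | 0.120 |
| 0.75 | 1.68 | 0.18 | 1.53 | 0.21 |
| 0.50 | 1.12 | 0.32 | 1.02 | 0.35 |
| 0.25 | 0.56 | 0.57 | 0.51 | 0.60 |
| 0 | 0 | 1 | 0 | 1 |

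The largest expected loss, at f = 0, is about 2 patients per term.

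**4. Whether the loss would show.** The exact 95% interval is 0.9% to 23.5% for 2/28 (7.1%) and 0.1% to 18.4% for 1/28 (3.6%). Both contain 8% and 7.3%, so the loss of one case could not be told from chance.

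**5. Grade 1–2.** Section 8.1 gives no laboratory rates below grade 3, so the loss there cannot be put into numbers from these documents.

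**The case against.** The strongest reply is that 8.3 and 12.4(c) agree with each other. One defines an adverse event and the other tabulates adverse events so defined. That is correct. This is not a contradiction but a limit on what the table measures, and no decision in Section 12 depends on those counts.

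The second reply is that 8.3 is broad. Further diagnostic testing alone qualifies a value, and a severe ALT rise would often lead to some. Corrective treatment of anemia would also qualify. This stands in part: it makes loss at grade 3–4 uncertain for ALT and less likely for anemia. It does not reach low-grade values, and it leaves the count dependent on what was ordered.

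Two stronger readings are tempting. A reader might infer that the table will fall short of the protocol's own benchmark rates. The documents do not support this. Section 8.1 serves expectedness, 12.4(c) plans no comparison with it, and nothing says how its source captured laboratory events. A reader might also infer that severe cytopenias drop out generally, because four of the ten grade 3–4 rates in 8.1 are laboratory-defined (neutropenia, thrombocytopenia, anemia and ALT). The actions in 7.1, 7.1b and 9.1.4 answer most of that for neutrophils, platelets and hemoglobin.

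**Conclusion.** The point holds in a limited form. Laboratory rows of the safety table depend on symptoms, action or therapy and not on grade, so they can under-report and cannot over-report relative to a count by grade. ALT/AST rises and grade 1–2 abnormalities are the most exposed.

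At grade 3–4 the most that could be lost is about 2 patients each for anemia and ALT. That bound assumes the 8.1 rates apply to this population and that no such case is captured. The true share is unknown, and for anemia complete loss is unlikely given 9.1.4. Sample size, error rates and the response endpoint are untouched. This is a worthwhile, inexpensive improvement to the reporting of a secondary endpoint.

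Separately, 7.6 excepts anemia from dose reduction, while 9.1.4 lists low hemoglobin among reasons to reduce irinotecan. These passages must be reconciled, because whether a hemoglobin value becomes an adverse event under 8.3 turns on which one is followed.

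**What to change.** Keep 8.3 for adverse-event reporting and add to 12.4(c):

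> The worst CTCAE v4.0 grade per patient for each gradable hematology and chemistry analyte on the study calendar will be derived from all recorded values, whatever their adverse-event status, and tabulated separately from reported adverse events.

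Add a table note that scheduled samples are taken at the start of each cycle, so counts of nadir toxicity are a lower bound. The extra table does not remove that limit.

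The cost is one more table and no new visit or blood draw, because the tests are already scheduled. Section 13 does not say whether numeric laboratory results are entered on the case report forms. Any not already in the trial database would have to be entered, including unscheduled results if they are to count as recorded.

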## 8.4 Routine Adverse Event Reporting

All Adverse Events **must** be reported in routine study data submissions. All serious adverse events and AESIs (initial and follow-up information) will be reported on FDA Medwatch (Form 3500A) or Suspect Adverse Event Report (CIOMS Form 1) IRB Reporting Form. The SAEs that are subject to this reporting provision are those that occur from after the first dose of the Study Drug through 30 days after discontinuation of the Study Drug. All serious AEs will be reviewed by the Protocol Monitoring committee (see section 14.3.3).

All serious adverse events that have not resolved by the end of the study, or that have not resolved upon discontinuation of the subject's participation in the study, must be followed until any of the following occurs:

- The event resolves;
- The event stabilizes;
- The event returns to baseline, if a baseline value/status is available;
- The event can be attributed to agents other than the study drug or to factors unrelated to study conduct;
- It becomes unlikely that any additional information can be obtained (subject or health care practitioner refusal to provide additional information, lost to follow up after demonstration of due diligence with follow-up efforts).

## 9. PHARMACEUTICAL INFORMATION

### 9.1 Drug Formulation, Storage, Availability, Preparation, Toxicity

All the drugs on the FOLFIRINOX regimen (5- fluorouracil, leucovorin, irinotecan and oxaliplatin) are available commercially therefore we do not anticipate any problems in delivering the drugs to patients. The drugs will be administered per institutional guidelines.

#### 9.1.1 Oxaliplatin

##### *Availability*

Oxaliplatin is commercially available as an aqueous solution in vials containing 50 mg and 100 mg at a concentration of 5 mg/mL. The vials do not contain any preservative and they are intended for single use.

##### *Storage and Stability*

Intact vials should be stored at room temperature. Solutions diluted in D5W are stable for 6 hours at room temperature or 24 hours under refrigeration.

##### *Preparation*

The calculated dose of oxaliplatin should be diluted for infusion with 250 mL to 500 mL D5W. Oxaliplatin should not be diluted with a sodium chloride solution. Needles, syringes, catheters or IV administration sets containing aluminum should not be used with oxaliplatin. As with other platinum compounds, contact with aluminum may result in a black precipitate.

##### *Administration*

Oxaliplatin will be administered by intravenous infusion over 120 minutes in patients receiving FOLFOX. Infusion time may be prolonged (up to 6 hours) in patients experiencing pharyngolaryngeal dysesthesia.

Oxaliplatin is unstable in the presence of chloride or alkaline solutions. Do NOT mix or administer oxaliplatin with saline or other chloride-containing solutions. Do NOT administer other drugs or solutions in the same infusion line. Flush IV lines/catheters with Dextrose 5% in Water both before and after oxaliplatin administration.

##### *Toxicity*

The most commonly observed oxaliplatin toxicities include neurotoxicity, GI toxicity, and myleosuppression. Three neurotoxicity syndromes have been seen:

Acute sensory neuropathy develops within hours to 2 days after oxaliplatin administration. Symptoms include paresthesias, dysesthesias, and hypoesthesia of the hands, feet and perioral regions. Jaw spasm, abnormal tongue sensation, dyarthria, eye pain and a sensation of chest pressure have also been noted. Acute sensory neuropathy symptoms may be exacerbated by exposure to cold temperature or cold objects. Symptoms are reversible, usually resolving within 14 days and commonly recurring with further dosing. This syndrome has been observed in about 56% of patients receiving oxaliplatin with 5-FU and leucovorin.

Acute pharyngolaryngeal dysesthesia is reported to occur in 1-2% of patients. This syndrome is characterized by a subjective sensation of difficulty breathing or swallowing without laryngospasm or bronchospasm or objective evidence of hypoxia. Avoidance of cold drinks, food and air is suggested to order to minimize pharyngolaryngeal

dysesthesia. Antianxiety agents (e.g. lorazepam) may be used to treat pharyngolaryngeal dysesthesias once oxygen saturation has been documented to be normal.

Peripheral neuropathy persisting > 14 days is characterized by paresthesia, dysesthesias, and hypoesthesia. Abnormalities in proprioception may also be seen. Symptoms of persistent neuropathy may improve upon discontinuation of oxaliplatin.

Various agents have been used in an attempt to minimize neurotoxicity of oxaliplatin (e.g. carbamazepine, pregabalin). Their routine use requires further confirmation of efficacy. They may be used in this study at the discretion of the treating physician.

Gastrointestinal toxicities include nausea, vomiting (oxaliplatin is considered to be moderately emetogenic) and diarrhea.

Neutropenia is reported in 73% of patients receiving oxaliplatin with 5-FU and leucovorin (44% grade 3 or 4). Grade 3 or 4 thrombocytopenia is reported to occur in 4% of patients receiving the combination.

Allergic reactions, similar to those seen with other platinum compounds, have also been observed in patients treated with oxaliplatin. Reactions range from rash to anaphylaxis

Rarely, oxaliplatin has been associated with pulmonary fibrosis, which may be fatal. Oxaliplatin should be discontinued in the presence of unexplained pulmonary symptoms (e.g. nonproductive cough, dyspnea) or pulmonary infiltrates until interstitial lung disease or pulmonary fibrosis have been ruled out.

Recent reports of oxaliplatin extravasation suggest that tissue necrosis may result and that oxaliplatin should be considered a vesicant. No standard treatment exists for oxaliplatin extravasation although heat and sodium thiosulfate have both been suggested.

Veno-occlusive disease (VOD) of the liver is a rare complication associated with oxaliplatin and 5-FU. Clinical manifestations of VOD include hepatomegaly, ascites, and jaundice. Histologically, VOD is characterized by diffuse damage in the centrilobular zone of the liver. Sequelae of VOD include hepatomegaly, splenomegaly, portal hypertension, and esophageal varices. A recent analysis of resected liver metastases in 153 patients indicated histological findings consistent with VOD in 6/27 patients who received 5-FU alone, 4/17 patients who received 5-FU and irinotecan, 20/27 patients who received 5-FU and oxaliplatin, and 14/16 who received 5-FU, oxaliplatin and irinotecan. The remaining 66 patients had not received chemotherapy prior to resection. There were no such findings in these patients.

For more information on toxicities associated with oxaliplatin, please see the package insert.

### **9.1.2 5-Fluorouracil (5-FU: fluorouracil: Adrucil®)**

#### *Availability*

5-FU is commercially available as a 50 mg/mL solution for injection in 10 mL, 20 mL, 50 mL and 100 mL vials

#### *Preparation*

Inspect for precipitate: if found, agitate or gently heat in water bath.

46-48 hour infusion of 5-FU should be prepared for administration via ambulatory infusion pump according to the individual institution's standards. These solutions may be prepared in D5W or 0.9% NaCl. 5 FU should not be mixed in the same solution with most parenteral anti-emetics.

#### *Storage and Stability*

Intact vials should be stored at room temperature and protected from light. Slight yellow discolor does not usually indicate decomposition. Stability in ambulatory pumps varies according to the pump, manufacturer of drug, concentration and diluent. Please refer to appropriate reference sources for additional information.

#### *Administration*

In this study, 5-FU is administered as 2400 mg/m^2 by IV infusion over 46 to 48 hours.

#### *Toxicity*

Nausea, diarrhea, vomiting (mild); stomatitis (5-8 days after treatment initiation); myelosuppression; granulocytopenia (9-14 days); thrombocytopenia (7-14 days); alopecia; loss of nails; hyperpigmentation: photosensitivity; maculopapular rash; palmar-plantar erythrodysesthesias: (42-82% receiving continuous infusion); CNS effects: cerebral ataxia (rare); cardiotoxicity: MI, angina: asymptomatic S-T changes 68%; ocular effects: excessive lacrimation and less commonly, tear duct stenosis.

#### *Drug Interactions*

Leucovorin enhances the cytotoxicity of 5-FU by forming a more stable tertiary complex with thymidylate synthase. Concomitant administration of 5-FU with warfarin has been reported to result in increased INR/prolonged prothrombin time. Patients receiving both drugs should be followed with weekly INRs.

Please refer to the package insert for complete product information.

### **9.1.3 Leucovorin Calcium (Folinic Acid; calcium folinate; citrovorum factor; N 5-formyltetrahydrofolate; 5-formyl-FH4; folinic acid).**

#### *Availability*

Leucovorin calcium is commercially available in: 50 mg, 100 mg, 350 mg vials for reconstitution.

#### *Storage and Stability*

Intact vials should be stored at room temperature and protected from light. Solutions reconstituted with BWI are stable for at least 7 days at room temperature.

#### *Preparation*

Leucovorin may be reconstituted with Bacteriostatic Water for Injection (BWI) or with Sterile Water For Injection. Solutions should be further diluted in D5W, 0.9% NaCl or Ringers solution for infusion over two hours.

#### *Administration*

Leucovorin will be administered as a 400mg/m^2 IV infusion over 2 hours after oxaliplatin administration. Leucovorin may also be administered concurrently with oxaliplatin as a separate IV infusion.

#### *Toxicity*

The only adverse reactions associated with leucovorin are allergic reactions. These are extremely uncommon.

Please refer to the package insert for complete product information.

### **9.1.4 Irinotecan (CPT-11, Camptosar).**

#### *Availability*

Irinotecan is commercially available in a concentration of 20mg/mL in 2mL, 5mL, and 25 mL vials.

#### *Storage and Stability*

Intact vials should be stored at controlled room temperature 59 to 86 degrees Fahrenheit (15 to 30 degrees Celsius) and protected from light. Solutions diluted in D5W are reported to be stable for 48 hours under refrigeration and protected from light. Irinotecan solutions should not be frozen as the drug may precipitate.

#### *Preparation*

Irinotecan is diluted in 5% dextrose (D5W) 500 mL to a final concentration of 0.12 – 1.1 mg/mL.

#### *Administration*

In this study, irinotecan is administered by IV infusion over 90 minutes

